b. Steps taken to minimize the risks.

After obtaining consent, all participant data (such as basic demographics and contact information) is entered into the emocha platform. In addition, HIV surveillance data is imported into the emocha platform from the BCDH (see above). Risks to confidentiality will be minimized by storing all data in encrypted format on an emocha web-server that is password protected. Data collected by the LTCR emocha app will be sent in real-time to a secure server, where LTCR activities and data can be accessed through a simple web interface. Only authorized study personnel will have access to this data. A triple level of data encryption will be used to ensure confidentiality of data and HIPAA-compliance. LTCR phones, and access to the LTCR and participant emocha apps will be password protected. To further protect participants' confidentiality, messages to the participant will include non-specific terms without mention of HIV or other personal health information. Electronic research data will be exported from emocha to central storage (JHU) via secure, encrypted transmission. The National Center for Health Statistics is required by law to maintain the confidentiality of identifying information it collects including information on individuals supplied by research groups to the National Death Index for the purpose of matching study participants to death records.

c. Plan for reporting unanticipated problems or study deviations.

The research staff and support staff will report problems or study deviations to the study supervisor ([name]). [name] will discuss problems and event with the study PIs (Drs. [name] and [name]) at weekly study meetings (or sooner) depending on the severity of the event. The PIs will report unanticipated problems or study deviations that involve risks to participants or others promptly to the JHM IRB in accordance with Organization Policy. Minor problems and protocol deviations (which pose no risk to subjects or others) will be reported in annual protocol continuing review.

d. Legal risks such as the risks that would be associated with breach of confidentiality.

There are risks that confidential information could be revealed to people not involved in the research such as a friend, relative, or an outside organization. This could be embarrassing to the participant if the participant wanted to keep participation in the study secret. The legal risks are limited because we are not collecting any additional data than is collected during routine BCDH activities. Thus, the risks associated with participating in this study are no greater than the risks associated with routine psychological examinations or tests.

e. Financial risks to the participants.

This study entails no financial risks to participants.

5. Benefits

a. Description of the probable benefits for the participant and for society.

The study has the potential to benefit society if the tested intervention (nHealth LTCR) is found to be effective in improving virologic suppression by reducing HIV transmission risk in the community.

6. Payment and Remuneration

a. Detail compensation for participants including possible total compensation, proposed bonus, and any proposed reductions or penalties for not completing the protocol.

Participants will receive \$50 for completing the baseline enrollment and \$20 for completing client satisfaction surveys. Participants randomized to the intervention arm who do not own a phone will be provided a study phone with a pre-paid data plan.

Participants in the in depth interviews will be compensated \$50 for their time.

7. Costs

a. Detail costs of study procedure(s) or drug (s) or substance(s) to participants and identify who will pay for them.

There will be no costs to participants for any services or treatment provided in this study. The study procedures will be financed by a PCORI grant.

References

ⁱ Flynn C. Baltimore City HIV Annual Epidemiologic Profile. Available at <https://phpa.health.maryland.gov/OIDEOR/CHSE/SiteAssets/Pages/statistics/Baltimore-City-HIV-Annual-Epidemiological-Profile-2016.pdf>

ⁱⁱ Flynn C. Maryland Annual HIV Epidemiologic Profile. Available at <https://phpa.health.maryland.gov/OIDEOR/CHSE/SiteAssets/Pages/statistics/Maryland-HIV-Annual-Epidemiological-Profile-2015.pdf>.

ⁱⁱⁱ Shah M, Perry A, Risher K, et al. Effect of the US National HIV/AIDS Strategy targets for improved HIV care engagement: a modelling study. *Lancet HIV* 2016; **3**(3): e140-6.

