Laboratory Data	HIV surveillance data (Viral load and date) is provided by the BCHD and uploaded to emocha platform	
Laboratory Alerts	Support staff is alerted if participant in the intervention arm has not had a viral load in > 4 months or if the viral load is detectable (> 200 copies/ml)	Support staff contacts participant if alerted
Appointment Alerts	Support staff alerted if no upcoming appointment is documented in the emocha app or the patient responds "No" or does not respond to the question "Did you go to your appointment yesterday" or patient requests help rescheduling appointment	Support staff contacts participant if alerted
Patient initiated messages	Support staff alerted when participant sends message	Support staff contacts participant if alerted

Study Design.

This study is a pragmatic individual randomized trial comparing standard BCHD linkage services or clinic-based linkage and retention and care support services to mLTCR services. The study will not be masked to participants or support staff due to practical considerations, but all data analysis related to Aim 1 will be conducted in a blinded fashion. Figure 2 describes the study design.

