
HIV Surveillance Data Flow. HIV laboratory data (dated viral load) will be used to drive emocha app alerts and for evaluation of primary outcomes. A list of the individuals who have consented to the study (including those recruited in the clinics) will be provided to the BCDH on a weekly basis. The BCHD will send this information to the Maryland Department of Health HIV Surveillance Branch. MDH will generate a weekly report of HIV viral load test results and dates and send this information to the BCDH. The BCDH will share this information with emocha so that it can be uploaded to the emocha platform. Alerts to participants will not include HIV-specific information. HIV surveillance data will be uploaded to the

emocha platform for all participants (intervention and control) and used for data analysis. However, this data will be integrated into the emocha algorithms and alerts only for participants in the intervention arm. Data on all participants will be exported from emocha to JHU secure servers for data analysis.

A backup system will be implemented in the event the MDH or BCHD is unable to generate and/or share the weekly HIV viral load test results. Study team members will access viral load data through health provider records and upload data directly from JHU secure servers to the emocha platform.

Laboratory Assessments. There will be no study-associated laboratory assessments. All laboratory assessments will be conducted as part of clinical care and reported to BCHD HIV surveillance databases (eHARS and PRISM). We will consider those with a suppressed viral load (HIV RNA <200 c/mL) to be fully engaged in HIV care. While some individuals are able to maintain immune control of HIV in the absence of ART, this occurs in <1% of infected persons.

Randomization plan. The study Statistician will generate a randomization schedule to assign 250 participants to each of the study arms with an arbitrary labelling of the arms. All but the data manager will be blinded to the arm assignment to the arbitrary labels initially. When a linkage officer makes the initial contact with an eligible participant /patient, they will introduce the study and if consent to participate is obtained, the officer will telephone the data center to obtain an arm assignment and proceed to enroll the participant. All data analysis will be conducted in a blinded fashion, but the linkage officers and participants cannot be masked from the intervention.

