- b. Secondary outcome variables.
 - 1. Retention in care: Viral load or CD4 count reported in eHARS within a 6 month window of 12 month follow up period (i.e. 3 months before or after 12 month follow up)
 - 2. Mortality: Death occurring within a 6 month window of 12 month follow up period (i.e. 3 months before or after 12 month follow up)
 - 3. Implementation outcomes will include:
 - a. Proportion of out of care or newly diagnosed HIV-infected patients contacted by support staff.
 - b. Frequency of contacts between support staff and patients.
 - c. Qualitative assessments from in-depth interviews with support staff, BCHD/clinic officials, and study participants
 - d. Client satisfaction surveys
- c. Statistical plan including sample size justification and interim data analysis.

Statistical Analysis. For the study's main outcome, we will conduct a test for the equality of proportions of virologically suppressed/not suppressed or missing VL individuals at 12 months between the two study arms, in line with the randomized design of the study. Secondary to this, and to adjust for any residual confounding, we will conduct a logistic regression using individual outcomes (yes/no suppressed) with study arm as a main predictor and adjusting for patient demographic characteristics, socio-economic status at baseline, and other factors. A subgroup analysis will be conducted to assess the effects of the intervention among African-American and people of Hispanic/Latino descent.

Secondary outcomes analysis. An evaluation of the differences in retention in care and participant mortality will follow the same analytical approach as for the main outcome. That is, we will test for the difference in proportions between the 2 arms and a logistic regression will be conducted adjusting for study arm and patient characteristics.

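### The Aim 1 data for both arms come from the app platform, whose missing-viral-load alert runs in one arm only, so results lost in transfer can be made good in the intervention arm but not in control

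*Combined protocol and SAP*

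**What the plan says.** The HIV Surveillance Data Flow paragraph in section 4.a gives one laboratory feed two purposes: "HIV laboratory data (dated viral load) will be used to drive emocha app alerts and for evaluation of primary outcomes". MDH produces a weekly report of viral load values and dates, BCHD receives it and passes it to emocha, and it is uploaded for both arms. The analysis file is the platform's copy: "Data on all participants will be exported from emocha to JHU secure servers for data analysis".

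The feed is active in one arm only: "However, this data will be integrated into the emocha algorithms and alerts only for participants in the intervention arm". Table 2 gives the trigger, "Support staff is alerted if participant in the intervention arm has not had a viral load in > 4 months" or when the value is above 200 copies/ml, and a single response: "Support staff contacts participant if alerted". Control participants have no further study contact apart from a satisfaction survey and a possible interview.

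Section 7.a defines the primary outcome as a viral load below 200 within 3 months either side of month 12, that is, months 9 to 15. Section 7.c specifies a "test for the equality of proportions of virologically suppressed/not suppressed or missing VL individuals at 12 months between the two study arms", so a missing result counts against the arm in which it occurs.

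The data-flow paragraph has a backup using provider records, but only for when MDH or BCHD cannot generate or share the weekly report. Nothing describes checking the emocha export against eHARS, the state HIV reporting system, in either arm.

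**The concern.** The alert for a missing viral load is part of the intervention, but it also acts as a completeness check on the outcome data, and it operates in one arm. A participant may have been tested and suppressed, with the result held by MDH, and the record may then be lost between MDH, BCHD and emocha. In the intervention arm the platform sees a gap, staff contact the participant, and a repeat test can put a suppressed value on file. In control the same loss raises no platform alert, and the participant is scored as a failure.

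That difference reflects record-keeping, not health. It adds to the apparent effect in the intervention's favour, and the planned file cannot separate it from real benefit.

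**Working it through.** **Inputs from the documents.** Control rate 33%, target 46%, 80% power, alpha 5%, 221 per arm (section 7.c, Power Calculations); 250 per arm randomised (section 4.a, Randomization plan). I read the 33% as the share with a viral load who are suppressed, which is how the same paragraph defines success in the other arm. The test is not stated to be two-sided; I take it so because that reproduces the sample size.

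**The plan's own figure.** With pooled variance, no continuity correction and a mean rate of 0.395:

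n = [1.96·√(2·0.395·0.605) + 0.8416·√(0.33·0.67 + 0.46·0.54)]² / 0.13² = 220.8, so 221 per arm and 442 in total. This agrees with the plan. Power is 80.0% at 221 per arm and 84.7% at 250.

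**Assumptions, because the documents give no figures.** Let m be the share of truly suppressed participants for whom *every* qualifying result in months 9 to 15 is lost after MDH. This is smaller than the share of individual results lost, because another suppressed result in the window covers a single loss. Let f be the share of these restored in the intervention arm, with none restored in control. There is no true effect, and true suppression is p = 0.33 in both arms.

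- Observed control rate: pC = p(1 − m)
- Observed intervention rate: pT = p(1 − m(1 − f))
- Spurious difference: d = pT − pC = p·m·f
- S0 = √(2·p̄(1 − p̄)/250), with p̄ the mean of pC and pT
- S1 = √([pC(1 − pC) + pT(1 − pT)]/250)
- Type I error = P(Z > (1.96·S0 − d)/S1) + P(Z < (−1.96·S0 − d)/S1)

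**Worked case, m = 5%, f = 1.** pC = 0.33·0.95 = 0.3135; pT = 0.33; d = 0.0165; p̄ = 0.32175; S0 = 0.04178; S1 = 0.04178. The two tails are P(Z > 1.565) = 0.0588 and P(Z < −2.355) = 0.0093, which sum to 0.0680.

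| m | Suppressed participants affected per arm (of 82.5) | d, f = 1 | Type I error, f = 1 | d, f = 0.5 | Type I error, f = 0.5 |
|---|---|---|---|---|---|
| 2% | 1.7 | 0.66 points | 5.28% | 0.33 points | 5.07% |
| 5% | 4.1 | 1.65 points | 6.80% | 0.83 points | 5.45% |
| 10% | 8.3 | 3.30 points | 12.48% | 1.65 points | 6.85% |

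**Contrast.** If losses stay uncorrected equally in both arms (f = 0), d is 0 and type I error stays at 5%. The cost is then power: with true rates of 33% and 46% and 250 per arm, it falls from 84.7% to 83.5%, 81.6% and 78.2% at m = 2%, 5% and 10%. The bias therefore comes from the difference between arms in recovery, not from loss as such.

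**The case against.** The strongest reply is that no route from alert to corrected record is written down. Staff contact the participant; nothing lets them edit or re-request a platform record. That stands. A reader might infer that any lost or mismatched result is repaired in the intervention arm, and the documents do not support that. A late report can still arrive through the weekly feed in either arm. A persistent name mismatch could swallow the repeat test too. An error raises an alert only if it leaves a gap of more than 4 months or shows a value above 200. The intervention ends at month 12, so losses in months 12 to 15 have no study-specified alert in either arm. What remains is a loss in transfer followed by a repeat test that reaches the file.

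Second, contact after a missed viral load is what the intervention is meant to deliver. This also stands: a repeat test after a true gap is an intervention effect. Only a repeat prompted by a false gap, in someone already tested and suppressed, is artefact.

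Third, controls are not wholly unwatched. The MDH Out of Care report and clinic Data-to-Care reviews (section 4.a, usual care) can expose gaps in the registry or the clinic record in either arm. They would not reveal a result that MDH holds but emocha does not.

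A reader might also infer that the Aim 1 analysts are unmasked, since app messages and alerts are generated only in the intervention arm. The plan says "all data analysis related to Aim 1 will be conducted in a blinded fashion" and uses arbitrary arm labels. No passage says that app-use fields enter the analysis file, and none excludes them. This is a gap to close, not a demonstrated breach.

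**Conclusion.** The point holds in a limited form. The documents establish that one feed serves alerts and outcome, that the platform export is the analysis file for both arms, that alerts run in one arm, and that missing counts as failure. They also describe no reconciliation. The bias favours the intervention and arises only when a suppressed participant has every qualifying result lost between MDH and emocha.

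Its size cannot be determined from the documents. With full recovery in one arm and none in the other, it is negligible at a 2% loss, modest at 5%, and about a quarter of the 13-point target effect at 10% (3.3/13). Those are upper figures for each loss rate, and the loss rates are assumptions. A reader might take the 12.5% type I error as a finding about this trial; it is only the top of an assumed range. The stated sample size is unaffected. The change is worth making because it is cheap, not because serious bias has been shown.

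**What to change.** Use the platform copy for alerts only. Take the viral load and retention outcomes from one cumulative MDH/BCHD (eHARS) extract of viral loads and CD4 counts for all randomised participants. Pull it after the last participant's window closes, match it without knowledge of arm, and send it to the data manager. If provider-record results were obtained under the backup, add them by the same rule in both arms. Compare the extract with the emocha export and report discrepancies by arm; that also shows how large the problem was. State that the masked Aim 1 file contains no app-use fields.

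The extract meets a second need. Section 7.b defines retention by a viral load or CD4 count reported in eHARS, while the weekly feed is described as carrying viral loads and dates only.

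The cost is one further pull from a source that already supplies the trial, a wording change in the data-flow paragraph, and possibly an amended data-use agreement. The analysis must wait for the extract. It does not cure mismatches inside the registry itself.

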The BCHD identifies newly diagnosed patients with HIV or those who are out of care based on laboratory-based HIV surveillance report. In addition, clinics and providers can identify patients in need of retention services and refer patients to their clinic's patient navigators or the BCHD linkage to care program. HIV Clinics can also get assistance from study team members in identifying patients by sharing the "Data-to-Care" report. Using the report, study team members will identify patients in need of retention services and alert their providers. Providers can then refer the patients to their support staff, clinic's patient navigators or the BCHD linkage to care program. Support staff reach out to the patient identified through surveillance or referred by providers to offer linkage and retention and care support services. When support staff meet or talk with the patient, he/she will tell them that they may be eligible for a study and ask them for permission to be contacted by a study research assistant (RA). All patients, regardless of their interest in the study, will be linked to care by warm handoff per BCHD protocol or receive standard linkage and retention and care support services provided at the clinic. Support staff will call the study RA to let him or her know that there is a potential participant. The RA will meet or call the potential participant to go over the study. After obtaining and documenting written informed consent (for in person enrollment) or oral consent (for over-the-phone enrollment) of participants who wish to enroll in the study, the participant will complete a baseline questionnaire and the RA will use a randomization program that will electronically assign the patient to the control or intervention arm. Patients randomized to the control arm will have no further interaction with the study team other than receiving a satisfaction survey and potentially being invited to an in-depth interview (which they can decline). Participants randomized to the intervention arm will be instructed to download the app to their personal phones (or study phone if participant does not own a compatible phone) and practice using the app by messaging the support staff, ideally in the presence of the RA (this can be done by phone or videoconference), who can trouble shoot any issues and show the patient how to use the various features of the app. Participants in the intervention arm will continue to be in touch with support staff for 12 months using the app, and by phone or in person, depending on the participants needs and Covid-19 situation (as identified through the app algorithms and patient-generated messages).

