The control group will receive usual linkage and retention to care services provided by the BCHD or the participant's clinic. The objective of the trial is to determine the benefit of delivering mHealth enhanced, longitudinal linkage to care and retention services.

f. Definition of treatment failure or participant removal criteria.

Not applicable

g. Description of what happens to participants receiving therapy when study ends or if a participant's participation in the study ends prematurely.

Participants randomized to the intervention arm will receive mHealth-enhanced LTCR services for a year. Following the 12 month follow up, patients will receive usual BCHD LTC services or clinic-based retention and care services. The BCHD or clinics may decide to continue to provide mHealth-enhanced LTCR services beyond the patient's 12 month enrollment in the study based on the studies interim analysis of effectiveness, patient satisfaction and cost.

5. Inclusion/Exclusion Criteria

Enrollment criteria for RTC:

Eligibility criteria include:

1. ≥ 18 years of age
2. Ability to provide consent
3. Identified by BCHD Linkage protocol to be a new HIV diagnosis or HIV-infected and "out of care" or referred by HIV clinic-based patient navigator, nurse, or provider.

Exclusion criteria include:

1. Excluded due to insufficient facility using a smartphone based upon participant and/or study staff assessment during enrollment process.

Enrollment criteria for in-depth interviews

Participant meets one of the following criteria:

1. Participant in the RTC, OR
2. Linkage to care officer, OR
3. Patient navigator, OR
4. Other support staff members, e.g. nurses
5. Stakeholders at the Baltimore City Health Department (BCHD) who has administrative or programmatic input on HIV services

6. Drugs/ Substances/ Devices

a. The rationale for choosing the drug and dose or for choosing the device to be used.

Not applicable

- b. Justification and safety information if FDA approved drugs will be administered for non-FDA approved indications or if doses or routes of administration or participant populations are changed.
Not applicable
- c. Justification and safety information if non-FDA approved drugs without an IND will be administered.
Not applicable

7. Study Statistics

- a. Primary outcome variable. Virologic suppression: Viral load < 200 copies/cc within a 6-month window of 12 month follow up period (i.e. 3 months before or after 12 month follow-up).

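### Do the two descriptions of the randomisation step let people be excluded for poor smartphone skills after their arm is known?

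*Combined protocol and SAP*

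**What the plan says.** **Section 4a, Study Design.** "Support staff reach out to the patient identified through surveillance or referred by providers". They ask permission for a research assistant to make contact. The research assistant explains the study and obtains "written informed consent (for in person enrollment) or oral consent (for over-the-phone enrollment) of participants who wish to enroll in the study". Then "the participant will complete a baseline questionnaire and the RA will use a randomization program that will electronically assign the patient". App download and practice come after assignment, in the intervention arm only. A study phone is available to anyone without a compatible one.

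**Section 4a, Randomization plan.** "When a linkage officer makes the initial contact with an eligible participant /patient, they will introduce the study". If consent is given, "the officer will telephone the data center to obtain an arm assignment and proceed to enroll the participant".

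**Section 4b.** Support staff or a patient navigator collect basic demographic and contact details at the baseline visit.

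**Section 4f.** The item "Definition of treatment failure or participant removal criteria" is answered as not applicable.

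**Section 5, the only exclusion criterion.** "Excluded due to insufficient facility using a smartphone based upon participant and/or study staff assessment during enrollment process".

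**Section 7c.** The main test is one of equal proportions, for "virologically suppressed/not suppressed or missing VL individuals at 12 months between the two study arms, in line with the randomized design of the study". The power paragraph defines success as having a viral load and being suppressed.

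**The concern.** Two accounts of one step name different people and different systems, and nothing confines either to one recruitment route or period. The Study Design account covers both surveillance and provider referrals, so the health-department route appears to have two procedures.

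The sharper worry comes from combining sections. The Randomization plan puts enrolment after the arm is obtained, by an officer who cannot be masked. Section 5 makes the smartphone exclusion a judgement made during enrolment. Taken together, the wording could allow someone to be set aside after the arm is known. Only the intervention arm has to use the app, so such exclusions would fall mainly on that arm. If the people removed were less likely to be suppressed and were also left out of the analysis, the intervention would look better than it is.

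**Working it through.** **The plan's own figure.** Inputs from section 7c: 33% v 46%, 80% power, alpha 5% (taken as two-sided).

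n per arm = [1.96·√(2·0.395·0.605) + 0.8416·√(0.33·0.67 + 0.46·0.54)]² / 0.13² = (1.3550 + 0.5767)² / 0.0169 = 220.8, so 221 per arm and 442 in total, as stated. Power at 250 per arm is 84.7%. The order of randomisation steps does not enter this calculation.

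**The two accounts side by side.**

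| | Study Design | Randomization plan |
|---|---|---|
| Who obtains the arm | Research assistant | Linkage officer |
| How | Electronic program | Telephone call to a data center |
| Consent before assignment | Yes | Yes |
| Baseline questionnaire before assignment | Yes | Not mentioned |
| Smartphone check placed | Not explicitly | Not explicitly, but the patient is already called eligible |

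Person and system conflict. The order does so much less: silence about a questionnaire does not contradict its presence. Consent comes before the arm in both, so this is not a failure of allocation concealment.

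**When is the smartphone check made?**

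1. The Randomization plan starts from an eligible patient. Smartphone facility is the only exclusion listed in section 5, so a person who meets it is not eligible and does not reach the telephone call.
2. Study Design uses enrolment for the consent step, and the remuneration section uses it for the baseline. A check made during enrolment therefore fits before assignment.
3. Section 5 gives the judgement to the participant and/or study staff. Study Design distinguishes support staff from the research assistant, and the section on reporting problems separates research staff from support staff. If the judgement is the research assistant's, it belongs to the sequence in which assignment follows consent and questionnaire.

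**What would have to happen for bias.** Four things together: exclusion after assignment, concentration in one arm, poorer suppression among those excluded, and deletion from the denominator. None is stated. On the last, the text leans the other way. HIV Surveillance Data Flow sends a list of everyone who consented for viral-load reporting and uploads results for both arms. Section 7c groups missing viral load with not suppressed. Section 4f provides for no removals.

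**How large, if it did happen (assumed values, not in the documents).** Let e be the share of the intervention arm removed and r the suppression among them, with no true effect, 33% suppression and 250 assigned per arm. If they are deleted, the intervention proportion is q = (0.33 − e·r)/(1 − e). Type I error is for the two-sided pooled z test, normal approximation.

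| e | q − 0.33 at r = 0.20 | q − 0.33 at r = 0.10 | Type I error |
|---|---|---|---|
| 2% | 0.3 points | 0.5 points | 5.0–5.1% |
| 5% | 0.7 points | 1.2 points | 5.3–5.9% |
| 10% | 1.4 points | 2.6 points | 6.3–9.0% |

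Example: (0.33 − 0.10·0.10)/0.90 = 0.3556, which is 2.6 points. With r = 0.33 the difference is zero and the error 5.0%. If they stay in the denominator but their viral loads are not retrieved, the difference is −e·r: from −0.02·0.10 = −0.2 points to −0.10·0.20 = −2.0 points, against the intervention. Even the sign depends on assumptions that the documents do not supply.

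**The case for a change.** How the randomised groups are formed is core content, and a reader cannot tell from section 4a which procedure applies. The word eligible suggests earlier screening but does not say that the smartphone check is complete by then. Study Design does not place it either, and the first hands-on use of the app comes after assignment. Study phones solve lack of a phone, not lack of facility.

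Nor does any section say outright that everyone assigned is kept in the analysis. Section 7c raises 442 to 500 for withdrawals, an allowance of 58 people or 11.6%. If all withdrawals stayed in as not suppressed, that allowance would not be needed to keep 442 in the analysis. A few sentences would settle all of this at almost no cost.

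What stands is the conflict over person and system, and the fact that neither the timing of the check nor the analysis set is spelled out. What does not stand is the step from not explicit to a threat. The withdrawal allowance is a routine margin and does not say that people are deleted. The main test is tied to the randomised design and has a category for missing viral load, which is how an analyst would treat anyone who was set aside.

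**Conclusion.** No change to the plan is needed. The two accounts in section 4a disagree on who obtains the arm and by what system, and section 4b adds a further role at baseline. This is an inconsistency of drafting. Whichever account is followed, an eligible, consented person is assigned and then compared with the other arm under a rule that counts a missing viral load as not suppressed. Writing down one order and naming the analysis set would record what a competent team would do anyway. It would alter neither the design, nor the sample size of 442 (500 enrolled), nor the primary test.

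The possible bias has no basis for sizing in the documents. Under the assumed values it runs from 2.6 points in favour of the intervention to 2.0 points against it, and it is zero if everyone is analysed as assigned with their own viral load. The conclusion rests on reading eligible in its ordinary sense and on analysts following the section 7c rule. It would need revisiting only if trial records showed people excluded for smartphone facility after assignment and then dropped from the analysis.
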